## BACKGROUND

### 1) Discuss the following in paragraph format

- Discuss the importance of the topic (public health and/or clinical importance and impact on individuals/community; incidence, prevalence, mortality and morbidity)
- Critically appraise the relevant literature and discuss the state of current knowledge on the topic (including deficiencies in knowledge or gaps that make the study worth doing)
- Describe, in detail, your approach to address the research question
- Explain how your study will contribute to existing research and benefit other individuals or the wider community

**RESPONSE:** Mucolytics like n-acetylcystine have shown some success previously in the management of filamentary keratitis. There is no data evaluating whether Mucinex ® is also effective at decreasing severity. Anecdotally, patients have reported that filamentary keratitis symptoms improved with the use of mucinex ® for upper respiratory congestion. Filamentary keratitis is an uncommon (chronic) eye condition frequently associated with dry eye disease. Affected patients typically present with symptoms including foreign body sensation, grittiness, pain, photophobia, tearing and increased blink rate. On examination there are thread-like mucus filaments adherent to the corneal surface. Current management of filamentary keratitis addresses dry eye disease (lubrication, punctal plugs), inflammation (anti-inflammatory eye drops), mucous buildup (n-acetylcystine as a mucolytic) and filament removal with forceps. Previous histologic evaluation has demonstrated that the filaments consist of a corneal epithelial core wrapped in mucus. Staining has established that there is significant overlap in the mucins produced in the eye and those from the respiratory tract, most notably MUC5AC and MUC16. There are several proposed mechanisms for filament formation. The general process begins with an insult to the epithelium, Bowman's membrane, or both, and is commonly associated with some degree of aqueous tear deficiency. Primary treatment modalities include lubrication, filament removal, anti-inflammatories and mucolytics. Several past studies have shown limited success using n-acetylcystine for its mucolytic properties. To date there are no trials studying Mucinex ®, which is well-tolerated, cost-effective and has been shown to hydrate respiratory mucus secretions, in the treatment of filamentary keratitis.

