## ELIGIBILITY CRITERIA

**6a). Inclusion Criteria** - Inclusion criteria are the ‘characteristics’ that clearly describe the study population that are required for a subject to be included in the study. The criteria may be based on factors such as age, gender, the type and stage of a disease, previous treatment history, and co-morbid medical conditions. They may state appropriate criteria for admitting special ‘at-risk’ populations such as women of reproductive age, children or patients with disease states or organ impairment.

**RESPONSE:** 1) Patients 18 years or older who have filamentary keratitis in at least one eye. 2) Schirmers test  $\geq 3$ mm in the eye diagnosed with filamentary keratitis (can be one eye or both the eyes).

**6b. Exclusion Criteria** - Provide details of participants that will be considered ineligible to participate and justification for their exclusion. These criteria are not always clinical in nature, aiming principally to accommodate participants in a safe and ethical manner. Criteria may include circumstances that interfere with the participant's ability to give informed consent (diminished understanding or comprehension, or a language other than English spoken and an interpreter unavailable), contraindications to the study treatment(s)/procedure(s), taking certain concomitant medication(s), or conditions that interfere with a patient's ability to comply with all treatment(s)/procedure(s).

**RESPONSE:** 1) Less than 18 years or older than 80 years of age; 2) Patients unable to provide informed consent; 3) Patients unable to attend a follow-up visit within 4 ( $\pm 1$ ) weeks; 4) Active ocular surface infection of any type; 5) Recent ocular surgery ( $< 30$  days); 6) History of nephrolithiasis as Mucinex ® has been associated in rare cases to the development of kidney stones; 7) Schirmer test  $< 3$ mm (in study eye; can be one eye or both the eyes); 8) History of hypersensitivity to Mucinex ®; 9) Concurrent eye disease requiring immediate initiation of a new treatment (e.g., topical steroids); 10) Restrictions for water intake can exacerbate the risk of nephrolithiasis and thus patients taking oral Mucinex ® are instructed to take each dose with a generous amount of water.

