## STUDY PROCEDURES

**8)** In this section you need to clearly and comprehensively describe exactly what will happen to participants once they are enrolled in your study. Depending on the study it might include how potential participants will be approached, when they will be randomized, the frequency and duration of visits or whether they are expected to self-complete a daily diary at home, the duration of the study or follow-up, and any measurements taken at each visit (e.g. questionnaires, physical measurements, biological samples).

You should include precise details of the treatment(s)/intervention(s) intended for each group/participant. You should also provide details of any follow-up schedule (i.e. time between visits) and consider how you will monitor participants' adherence with the treatment schedule. You might also describe under which circumstances participants may be withdrawn and how this will occur. A schematic diagram or flow chart may be useful for this section.

**RESPONSE:** To test the hypothesis that Mucinex® administration will reduce the signs and symptoms of filamentary keratitis, patients with the diagnosis of filamentary keratitis will be enrolled. At the initial visit (Day #1), visual acuity, number of filaments on the cornea, schirmers test, ocular surface symptoms, these are standard, non-invasive common clinic procedures that will be recorded. The patient will then be instructed to continue their current medication regimen, with no alterations. The patient will then be given 600mg tablets of extended-release Mucinex® to take home, and will be instructed to take them twice a day with abundant water until the next visit in 4 weeks. If patient misses a dose, they are not required to make up for missed dose and can continue to take the next dose. At the follow up visit the visual acuity, number of filaments on the cornea, and ocular surface symptoms will be assessed.

The investigators will screen the patients for a history of nephrolithiasis, a contraindication of this therapy prior to their enrollment. Patients will continue their usual eye treatment regimen while participating in this study.

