# Cover Sheet

**Study Title: MUCINEX for Treatment of Filamentary Keratitis**

**NCT No: NCT02859246**

**Date: 7/21/2019**

## Statistical Analysis Performed

[name], et al.

The Ocular Surface 17 (2019) 565–570

[figure not shown]

Fig. 2. Graph showing the number of filaments at baseline and 4 weeks after the addition of oral guaifenesin. (A) Cumulative filament number in all patients who received oral guaifenesin. (B) Separate analysis for patients who only added oral guaifenesin as a new treatment at baseline and patients who received oral guaifenesin and an increase in topical corticosteroids simultaneously.

[figure not shown]

Fig. 3. Graph showing symptoms score (OSDI) at baseline and 4 weeks after the addition of oral guaifenesin. (A) Cumulative OSDI score in all patients who received oral guaifenesin. (B) Separate analysis for patients who only added oral guaifenesin as a new treatment at baseline and patients who received oral guaifenesin and an increase in topical corticosteroids simultaneously.

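### Exclusion 9 admits patients whose eye medication is already due on Day 1 to be increased, or added to for filamentary keratitis, although section 8 requires an unchanged regimen

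*Protocol*

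**What the plan says.** Protocol section 6b, item 9 excludes patients with "Concurrent eye disease requiring immediate initiation of a new treatment (e.g., topical steroids"). Item 5 excludes "Recent ocular surgery" within the past 30 days. The first inclusion criterion in section 6a is "Patients 18 years or older who have filamentary keratitis in at least one eye"; the second is a Schirmer threshold.

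Section 8 (Study Procedures) says that after the baseline measurements the patient is told to "continue their current medication regimen, with no alterations". It later adds: "Patients will continue their usual eye treatment regimen while participating in this study". It gives no rule for a patient whose regimen does change.

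Section 5 describes a non-randomized study without a control group, and section 14 plans a paired before-after test.

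The SAP (Statistical Analysis Performed, legends to Figs. 2 and 3) presents filament count and OSDI for everyone who received guaifenesin in panel A. Panel B separates those whose only new treatment at baseline was guaifenesin from "patients who received oral guaifenesin and an increase in topical corticosteroids simultaneously".

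**The concern.** Section 8 assumes that background eye medication stays fixed from Day 1 to the follow-up visit, so that guaifenesin is the only planned medication change between the two measurements. The eligibility list does not enforce that assumption. Section 8's sentence is an instruction given after enrolment. Item 9, the one criterion that might screen for an expected change, is drawn more narrowly.

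In a single-arm before-after comparison no concurrent group shares the effect of a background change. If a patient enters knowing that another ocular medication will be raised or added, the change in OSDI (primary outcome) and in filament count (secondary outcome) is the joint result of both medications. Item 9's own example is topical steroids, so the protocol already treats this kind of co-treatment as a reason not to enrol. The wording simply does not reach every case.

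**Working it through.** The check is mainly a reading of the text; the plan has no figure on this point to reproduce.

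**Step 1. Take item 9 apart.** It excludes only if three conditions hold together: the disease is concurrent, that is, other than the one under study; the need is immediate; and a new treatment is being started.

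**Step 2. Apply it to situations known on Day 1.**

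| Situation | Item 9 | Section 8 |
|---|---|---|
| Existing ocular medication to be increased before follow-up | Not excluded: nothing new is started | Cannot be met |
| Medication to be added for filamentary keratitis itself | Not excluded: not a concurrent disease | Cannot be met |
| New drug needed at once for dry eye | Arguably excluded, as dry eye is an associated disease | Does not arise if excluded |
| Taper already scheduled | Not excluded | Unclear: may be part of the existing regimen |
| Filament removal or punctal plugs planned | Not clearly excluded | Unclear: the instruction concerns medication |

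Only the first two rows show a patient who is eligible and yet unable to comply.

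**Step 3. Look for another criterion that closes the gap.** Section 6a covers age, diagnosis and Schirmer result. The rest of section 6b covers age, consent, attendance, infection, past surgery, kidney stones, Schirmer result, hypersensitivity and water intake. Item 5 looks only backward. None asks for a stable regimen or looks ahead to the follow-up visit.

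**Step 4. Compare with the SAP.** The legends identify patients with a corticosteroid increase at the same time as guaifenesin. Panel A covers all who received guaifenesin, so these patients are in the all-patient comparison. The legends give no reason for the increases.

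**Step 5. What can be said about size.** If k of n patients have a co-treatment that alone shifts the outcome by d, the all-patient mean change moves by k × d / n. With the planned n = 15 (section 13), and k assumed for illustration:

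- k = 3: 3/15 = 0.20 d
- k = 5: 5/15 = 0.33 d
- k = 7: 7/15 = 0.47 d

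The available text gives neither k nor d, so this shows how the bias scales and does not estimate it. A helpful co-treatment would flatter guaifenesin; a reduction in background treatment could act the other way.

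**The case against.** The strongest reply is that section 8 already contains the safeguard. An investigator who knows on Day 1 that medication must change can decline to enrol, and the steroid increases may simply be departures from section 8 that better eligibility wording would not have prevented. The SAP also shows the guaifenesin-only patients separately. In a 15-patient pilot, on this view, little is lost.

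Part of this stands. Nothing forces a site to choose between breaking section 8 and holding back care, and panel B does help interpretation. But declining to enrol is then left to discretion where a criterion could settle it. Panel B divides a small sample and is not foreseen in the protocol, and it does not repair the entry rule.

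Three stronger readings are tempting, and the documents do not support them:

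- **That planned procedures and tapers also contradict section 8.** The instruction concerns medication. The Background lists, as current management, "mucous buildup (n-acetylcystine as a mucolytic) and filament removal with forceps", along with punctal plugs, and section 8 lets usual eye treatment continue. A taper fixed before Day 1 can be read as part of that. These are ambiguities rather than contradictions.
- **That dry eye lies wholly outside item 9.** The Background presents it as a frequently associated disease, so a new drug needed for it at once arguably falls within the exclusion.
- **That the SAP proves patients entered through this gap.** It shows that increases occurred. It does not show why, and it says nothing of tapers or procedures.

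**Conclusion.** The concern holds in a narrow form. Item 9 leaves eligible a patient for whom an increase in an existing ocular medication, or added medication for filamentary keratitis itself, is already planned on Day 1, and that patient cannot follow section 8. The SAP confirms that altered steroid treatment reached the all-patient before-after analysis, where its effect cannot be separated from that of guaifenesin in the patients concerned.

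The conclusion rests on the ordinary meaning of item 9's three conditions and on the absence of any stable-regimen criterion. It needs no assumption about why the SAP's steroid increases were made. The size of the bias cannot be derived.

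A reader might also infer that a fixed regimen is all that attribution to guaifenesin requires. It is not: without a control group, regression to the mean and natural fluctuation remain even if no one's medication changes. The gap is worth closing because it is an avoidable source of confounding, but closing it does not make the design causal.

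**What to change.** Reconcile item 9 with section 8. Word item 9 so that a patient is ineligible if, at Day 1, a start of or change to ocular medication for any eye condition, including filamentary keratitis, is already planned before the follow-up visit. Allow re-screening once the regimen is stable.

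State in section 8 whether a pre-scheduled taper, and routine procedures such as filament removal and punctal plugs, count as continuing usual treatment or as an alteration. Either answer can be applied consistently; the present text settles neither. Excluding every planned ocular procedure would be a larger trade-off in an uncommon condition and is not needed for this point.

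The change is to one exclusion item and a clarifying sentence. Its cost is somewhat slower recruitment, with some patients entering later through re-screening. It concerns who is enrolled and sets no treatment rule. Because the SAP reports an analysis already carried out, the rewording can help only further enrolment or a successor study; it does not alter the data in hand.

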## STUDY OUTCOMES

**7a). Primary Outcome** - The primary outcome should be the most important and clinically relevant outcome (e.g. clinical, psychological, economic, or other) of the study. This is the measure used to answer your study aim. However, it is also the outcome used to calculate study sample size and power and test the primary research hypothesis. Generally, no more than 1-2 primary outcome measures are pre-specified. Primary outcome measures may be measured in various ways such as: binary (e.g. caesarean/no caesarean, blood loss  $\geq 500$ mL/blood loss  $< 500$ mL); continuous (e.g. weight - kg, blood loss - mL); ordinal (e.g. pain - mild, moderate, severe); time to event (e.g. survival), and counts (e.g. number of infections, number of events occurring).

**RESPONSE:** Reduction of symptoms according to the Ocular Surface Disease Index score after treatment with oral mucinex ® twice a day (total dose is 1.2 g/day) for 4 weeks

**7b). Secondary Outcome(s)** - Secondary outcome(s) are measures of additional or less important research interest. They may include additional clinical, psychological, economic, or safety outcomes (e.g. treatment related side effects/adverse events). However, as these endpoints are not used to calculate study power and sample size it is often not possible to draw robust conclusions from the results.

**RESPONSE:** Reduction in the number of corneal filaments after treatment with oral Mucinex ® twice a day (total dose is 1.2 g/day) for 4 weeks.

## STUDY PROCEDURES

**8)** In this section you need to clearly and comprehensively describe exactly what will happen to participants once they are enrolled in your study. Depending on the study it might include how potential participants will be approached, when they will be randomized, the frequency and duration of visits or whether they are expected to self-complete a daily diary at home, the duration of the study or follow-up, and any measurements taken at each visit (e.g. questionnaires, physical measurements, biological samples).

You should include precise details of the treatment(s)/intervention(s) intended for each group/participant. You should also provide details of any follow-up schedule (i.e. time between visits) and consider how you will monitor participants' adherence with the treatment schedule. You might also describe under which circumstances participants may be withdrawn and how this will occur. A schematic diagram or flow chart may be useful for this section.

**RESPONSE:** To test the hypothesis that Mucinex® administration will reduce the signs and symptoms of filamentary keratitis, patients with the diagnosis of filamentary keratitis will be enrolled. At the initial visit (Day #1), visual acuity, number of filaments on the cornea, schirmers test, ocular surface symptoms, these are standard, non-invasive common clinic procedures that will be recorded. The patient will then be instructed to continue their current medication regimen, with no alterations. The patient will then be given 600mg tablets of extended-release Mucinex® to take home, and will be instructed to take them twice a day with abundant water until the next visit in 4 weeks. If patient misses a dose, they are not required to make up for missed dose and can continue to take the next dose. At the follow up visit the visual acuity, number of filaments on the cornea, and ocular surface symptoms will be assessed.

The investigators will screen the patients for a history of nephrolithiasis, a contraindication of this therapy prior to their enrollment. Patients will continue their usual eye treatment regimen while participating in this study.

### **9) Randomization (if applicable)**

Include the method (including any software) used to generate the random allocation sequence. Describe type of randomization performed, ratio of assignment to groups, block size permutation and stratification if applicable. Explain the methods used to conceal group allocation until assignment. Also, include information on who will generate the allocation sequence and who will assign participants into their groups.

This section should also discuss if participants, the investigator, and those assessing/analyzing the outcome(s) will be blind (or masked) to group assignment or if the study will be an open-label study (investigators and subjects know their assigned group).

**RESPONSE: N/A**

**10) Study Specific Procedures:** List all procedures (interventions, tests, surveys, etc.) to be performed ONLY for research purposes.

**RESPONSE: None**

**11) Standard of Care Procedures:** Clearly list all standard of care (standard therapy) procedures (interventions, tests, etc.) to be performed regardless of the subject's enrollment in the study, but that will be included in the research assessment.

**RESPONSE:** 1) Dry eye symptoms assessment (Ocular Surface Disease Index questionnaire).

## MEASUREMENT TOOLS

**12)** It is essential to state how the data will be collected to assess the primary and secondary outcome(s) of the study (e.g. patient questionnaire, medical charts, routinely collected hospital/research database, biological specimens). Describe at what point(s) of the study data collection will occur. You should make statements that justify the validity of the study measure/instrument. If not, you will have to verify how you will ensure the validity and quality of data being collected. Also, mention here if you are going to have one or more assessors to collect data, their level of training/experience (or how they will be trained), and if you are planning to assess inter-rater reliability (if applicable).

**RESPONSE:** Data will be collected during the two clinical visits (baseline and follow-up), in which ocular surface symptoms score and number of corneal filaments will be recorded in a data collection sheet.

**13) Sample size and statistical power** - A sample size or power calculation should be performed. This calculation is used to estimate the number of subjects required to answer your primary study hypothesis with an accepted power. Conversely, it also allows you to estimate what power can be achieved with a limited number of participants. This number is calculated by specifying the magnitude of the effects that are expected (i.e. informed and clinically significant), variability of the measurements and the acceptable degree of type I and II errors. You need to specify the assumptions made for the calculation. It is recommended that you consult with a statistician for this section. Also keep in mind the estimated recruitment rate and whether you need to adjust for anticipated non-responders and losses to follow up.

### RESPONSE:

This will be a first-of-its-kind study evaluating an FDA approved and over-the-counter available drug (guaifenesin; Mucinex®) to treat cough as part of the symptoms of common cold. Our study will be the first to evaluate the effect of Mucinex® alleviating the symptoms of filamentary keratitis. No data are available to estimate the changes expected after initiation of Mucinex®. This is a pilot study and represents minimal to no risk to participants, and involves no additional procedures other than the routinely performed clinical assessments. In this pilot study we aim to enroll 15 participants.

**14) Statistical methods** - The statistical methods used for the study objectives/hypotheses (e.g. t-test, chi-squared, multivariate modeling) must be sufficiently detailed. If conducting a randomized controlled study, you should state whether methods will include an “intention to treat” (ITT) analysis, per protocol analysis, or both. An ITT analysis is preferred as it compares all subjects in the groups to which they were originally randomly assigned (despite withdrawal, treatment failure or cross-over). Consultation with a statistician is strongly recommended. [See Harvard Catalyst Statistical Consulting for more information.](#)

**RESPONSE:** We will use a paired T test or a Wilcoxon signed-rank test, depending on the distribution of the data, to assess whether there is a significant difference between pre- and post-therapy symptoms of filamentary keratitis.

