## Statistical Test of Hypothesis

We calculated the difference in the mean number of filaments and OSDI score between baseline and follow-up visits and evaluated their change over time. We used the paired-sample Wilcoxon signed-rank test if data did not follow a normal distribution and the paired Student t-test in the case of normally distributed data. For all the analyses we considered the average value of both eyes for all variables with the exception of symptom scores (OSDI), which were considered per patient. Data are presented as the mean  $\pm$  standard deviation (SD), a range for continuous variables, and percentages for categorical variables. A twotail P value of less than 0.05 was considered statistically significant in all statistical tests. The statistical analysis was performed using STATA 13.0 (StataCorp, College Station, TX).

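### Does letting the data choose between a paired t-test and a Wilcoxon test, with no interval named for the OSDI change, call for a change to the plan?

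*Protocol*

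**What the plan says.** Protocol section 7a defines the primary outcome as "Reduction of symptoms according to the Ocular Surface Disease Index score after treatment with oral mucinex", measured over 4 weeks. Section 14 gives the analysis in one sentence: "We will use a paired T test or a Wilcoxon signed-rank test, depending on the distribution of the data". Section 13 sets a target of 15 participants and explains why there is no power calculation: "No data are available to estimate the changes expected after initiation of Mucinex". Section 5 describes a single-group study with no control.

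The SAP, under Statistical Test of Hypothesis, applies the same rule in the past tense: "We used the paired-sample Wilcoxon signed-rank test if data did not follow a normal distribution and the paired Student t-test" otherwise. It describes the effect for both endpoints as follows: "We calculated the difference in the mean number of filaments and OSDI score between baseline and follow-up visits". Results are summarised as mean and SD, "a range for continuous variables, and percentages for categorical variables". The only inferential criterion is this: "A twotail P value of less than 0.05 was considered statistically significant in all statistical tests".

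Neither text names a normality test or a cut-off, or says whether the rule applies to visit scores or to paired differences. Neither names a confidence interval. The SAP section is headed "Statistical Analysis Performed"; its figures and the results text are not available.

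**The concern.** Three features together look like a weakness.

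- **Choice of test.** With about 15 pairs, the same data decide which test is used and then supply the p-value, under a criterion the reader cannot reproduce.
- **Test and estimate.** The Wilcoxon signed-rank test addresses the pseudomedian of the changes. If the changes are skewed, this differs from the mean, so a Wilcoxon p-value could be printed beside a mean difference it does not test.
- **Precision.** A first pilot with no prior data is most useful for the size and precision of the change it observes. A p-value alone gives neither, and SDs at the two visits do not give the SD of the change.

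At stake would be an inflated error rate, a p-value attached to the wrong quantity, or a pilot estimate that a later trial could not use for planning.

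**Working it through.** **Inputs.** The target n = 15 (Protocol 13) and two-sided 0.05 (SAP) come from the documents. They give no effect size, SD of change, analysed n or normality criterion, so the shapes of the changes and a Shapiro-Wilk switch at p < 0.05 are assumptions. The plan has no figure of its own to reproduce, because 15 is a bare target.

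**1. Does the data-driven choice distort the error rate?** Share of simulated samples rejecting at n = 15, with an exact signed-rank test and true mean change zero (40,000 samples per row; 20,000 for gamma):

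| Paired changes | t | Wilcoxon | Plan's rule |
|---|---|---|---|
| Normal | 0.050 | 0.048 | 0.051 |
| Heavy-tailed (t, 3 df) | 0.043 | 0.049 | 0.050 |
| Exchangeable exponential visits | 0.046 | 0.048 | 0.050 |
| Exchangeable lognormal visits | 0.039 | 0.046 | 0.046 |
| Gamma, shape 4 (moderate skew) | 0.059 | 0.061 | 0.065 |
| Exponential (strong skew) | 0.091 | 0.113 | 0.116 |

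The first four rows have symmetric changes. That includes exchangeable visits: if nothing differs between the visits, the change is symmetric about zero even when the scores are skewed. The rule then stays at or below 0.051. In the exponential row, a fixed t-test is already at 0.091. Of the further 0.025, the different target of Wilcoxon accounts for 0.113 − 0.091 = 0.022 and the switch for 0.116 − 0.113 = 0.003.

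**2. Does the choice cost power?** At a true change of 0.6 SD, for t / Wilcoxon / plan's rule:

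- Normal: 0.58 / 0.56 / 0.58.
- Heavy-tailed: 0.71 / 0.77 / 0.76.

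The rule loses at most 0.77 − 0.76 = 0.01 against the better fixed test. Against the rule, always using t would lose 0.76 − 0.71 = 0.05 under heavy tails. Always using Wilcoxon would lose 0.58 − 0.56 = 0.02 under normality.

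**3. How large could the gap between test and estimate be?** The gap is the mean minus the pseudomedian of the changes:

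- Symmetric: 0.
- Gamma, shape 4: about 0.08 SD. The assumed switch would pick Wilcoxon in only about 21% of samples.
- Exponential: 0.16 SD, which is 0.16 / 0.554 = 29% of the interval half-width derived next.

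**4. What does the unnamed interval amount to?** The half-width of the 95% t-interval for the mean change is t(0.975, n − 1)/√n, in SDs of the change:

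- n = 15: 0.554.
- n = 12 (assumed): 0.635.
- n = 10 (assumed): 0.715.

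If only visit SDs were published, the SD of the change would be the visit SD × √(2(1 − r)), assuming equal SDs at the two visits. For an assumed correlation r of 0.2 to 0.8 this factor runs from 1.265 to 0.632. The half-width at n = 15 then runs from 1.265 × 0.554 = 0.70 to 0.632 × 0.554 = 0.35 visit SD, a factor of two.

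That uncertainty disappears if the SD of the change is given. If the t-test was used, the mean difference, n and an exact p-value are enough: SE = difference / t, and the half-width is t(0.975, n − 1) × SE. For example, p = 0.05 at n = 15 corresponds to an interval from 0 to 2 × 0.554 = 1.11 SD.

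**The case for a change.** The strongest case for a change is that every textual point is correct and the remedy is cheap. No criterion, interval or estimate paired with Wilcoxon is named. Fifteen pairs are also a weak basis for judging normality: the assumed Shapiro-Wilk rule flags only about 27% of heavy-tailed samples and 21% of moderately skewed ones. In the exponential case a signed-rank interval covers its own target in 94.4% of samples but the mean in only 88.6%. Naming one test with its matching estimate and interval would take a sentence or two and no new patients.

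What stands is that the methods text is thin, and that a full report would give the paired OSDI change with its interval and say which test was used.

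The rest does not carry. Poor detection of non-normality does little harm when both candidate tests perform acceptably, as the symmetric rows show. The 88.6% belongs to an interval that neither document proposes, and the t-interval covers the mean in only 90.9% of the same samples. The exponential shape is an assumption with nothing in the documents behind it. Naming a test in advance is no longer possible for data already analysed. That an excerpt's methods paragraph lists no interval does not show that none was reported.

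**Conclusion.** No change to the plan follows. The protocol fixed both candidate tests and the basis for choosing between them, and the SAP did what the protocol said. For symmetric changes, at n = 15 and with an assumed Shapiro-Wilk switch, the rule keeps its error rate (0.046 to 0.051). In the two shapes examined for power, it gives up about 1 percentage point at most. Fixing a single test is a fair alternative with its own cost of about 2 to 5 points in the wrong shape.

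The mismatch between p-value and mean is conditional on two facts the documents do not show: that Wilcoxon was used, and that the changes were skewed. Its size runs from nothing to 0.16 SD over the shapes examined.

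The unnamed criterion and interval are details that an analyst fills in without difficulty, by checking the paired differences and reporting the mean change with its t-interval, or the Hodges-Lehmann change with its interval if Wilcoxon applied. Supplying them would sharpen the report but would not make the stated test or its conclusion wrong. This assessment rests on the assumed switch and shapes, and on about 15 analysed pairs; the actual number is not stated.
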